1.1.4 Licogliflozin

Licogliflozin is a selective and potent inhibitor of the sodium glucose co-transporters (SGLTs) 1 and 2 that decreases absorption of glucose in the gut and reabsorption in the kidney (Chao and Henry 2010). In the normal state, 90% of the filtered glucose is reabsorbed by SGLT2 in the proximal convoluted tubule cells of the kidney, with the remaining 10% reabsorbed by the SGLT1. Inhibition of SGLT2 results in glucosuria, decreased blood glucose and modest weight loss in healthy participants and participants with T2DM (Bays 2013). In addition to expression in the kidney, SGLT1 is also expressed in the small intestine where it is required for glucose and galactose absorption. Thus, inhibition of enteric SGLT1 results in reduction of glucose and galactose absorption (Turk et al 1991) which results in calorie wasting and other potential endocrine-based weight loss mechanisms. Combined SGLT1 and SGLT2 inhibition therefore offers the potential for improved efficacy over SGLT2 selective inhibitors in both lowering blood glucose and body weight.

Licogliflozin was administered to 76 healthy participants in the US, 36 healthy participants in Japan. Single doses of up to 350 mg and repeated doses of up to 300 mg/day for 14 days in healthy participants were generally safe and tolerated. Licogliflozin was also administered to 41 participants with T2DM and 127 obese participants in the US.

In study CLIK066X2101, single and multiple doses of licogliflozin induced glucosuria in healthy volunteers (HVs) and participants with T2DM, and significantly lowered glucose area under the time-concentration curve (AUC) after an oral glucose tolerance test (OGTT) in participants with T2DM. Licogliflozin was found to be tolerated, had in both healthy participants and participants with T2DM.

Treatment of normoglycemic and dysglycemic obese participants with 150 mg qd licogliflozin for 12 weeks in CLIK066X2201 was shown to be safe, and resulted in 5.7% reduction in body weight. Diarrhea was observed as a potential dose-limiting side effect in this study (He et al 2019). These studies are summarized in the LIK066 IB.

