6.4 Treatment blinding

This is a double-blind study: participants, investigator staff, persons performing the assessments, and Novartis clinical trial team (or delegates) will remain blinded to the identity of study treatments from the time of randomization (until final database lock), using the following methods:

- 2. Randomization data will be kept strictly confidential until the time of final database lock and will not be accessible by anyone else involved in the study with the exceptions in Table 6-4.
 - a. The randomization codes will be disclosed to an independent analysis team to prepare safety and efficacy reports for the DMC. The independent analysts will keep randomization data confidential until data base lock. Data will be shared with the study team under blinded conditions.
- 3. The identity of the treatments will be concealed by the use of placebo that are each identical in packaging, labeling, schedule of administration, appearance, taste and odor to the respective active treatment. Placebo capsules/tablet will be given in active treatment groups when needed to maintain blinding as described in Section 6.1.3.

A double-dummy design is used because the identity of the study treatment cannot be disguised, as the drug products are visibly different.

Unblinding will only occur in the case of participant emergencies (see Section 6.6.2) and at the conclusion of the study. Unblinding a single participant's treatment at a site for safety reasons (necessary for participant management) will occur via an emergency system in place at the site. As a result the participant should be discontinued from the study treatment.

At the time of safety review, the DMC will review unblinded reports created by an independent analysis team. More details will be provided in the DMC charter.

Table 6-4Blinding and unblinding plan

Time or Event				
Role	Randomizatio n list generated	Treatment allocation & dosing	Safety event (single participant unblinded)	Safety review
Participants	В	В	В	В
Site staff	В	В	UI	В
Novartis CTT	В	В	UI	В
Global Clinical Supply	UG	В	UI	В
Randomization Office	UI	UI	UI	UI
Unblinded Pharmacovigilance sponsor staff	В	UI	UI	В
Statistician/statistical programmer	В	В	UI	В
Data Monitoring Committee(DMC) and independent statistician/programmer supporting DMC	UI	UI	UI	UI
All other sponsor staff not identified above (i.e. trial team, project team, management & decision boards, support functions)	В	В	В	В

Key:

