Visit Name	Screening 1	Screening 2	Baseline	W2	W4	W8	W12	W16	W20	W24	W32	W40	W48	Unscheduled	Follow-Up W52
Visit Number	1	2	3	4	5	6	7	8	9	10	11	12	13	-	14
Days	-70 to -42	-42 to -1	0	14	28	56	84	112	140	168	224	280	336	-	364
Weeks	-10 to -6	-6 to 0	0	2	4	8	12	16	20	24	32	40	48	0	52
Study treatment completion information ²¹													x		
Study completion information															х

^X Assessment to be carried out at respective visit and data for assessment to be recorded in the source, clinical database or received electronically from a vendor
 ^S Assessment to be carried out and data for assessment to be recorded in the source documentation at the site only
 ¹ Vital signs (including blood pressure and pulse measurements)
 ² For any ECGs with safety concerns, two additional ECG must be performed to confirm the safety finding.

ſ

Novartis	Confidential
Amended Protocol Version 02 (Clean)	

° Biopsy

a). The liver biopsy can be performed any time during the 10 week screening period, and should only be performed in participants who fulfill Screening visit 1 eligibility criteria refer Section 8.3.1.8 for details.

b) Screening biopsy results confirming eligibility are required prior randomization. Plan for the biopsy visit accordingly. The Screening visit 2 assessment can be performed before the biopsy results are obtained.

c). Read by a central pathologist.

d). Week 48 biopsy optional if participant discontinues before 24 weeks treatment period.

⁶ Hepatitis B surface antigen (HBsAg); HCV antibody (Ab) – if detected, reflex to Hepatitis C RNA by PCR; Immunoglobulin M (IgM) Hepatitis A antibodies (IgM anti-HAV) see Section 8.4.2.6.

⁷ At screening visit 1 this also includes ferritin, transferrin saturation, iron, and if not historically available also Anti-nuclear antibodies (ANA), Anti-smooth muscle antibodies (ASMA) and Anti-mitochondrial antibodies (AMA), see Section 8.4.2.2

⁸ Coagulation parameters including APTT, PT, INR and TT and fibrinogen.

⁹ Amylase & lipase to be analyzed at screening & Baseline and subsequently if pancreatitis is suspected.

¹⁰ Dipstick measurements for color, clarity, specific gravity, pH, bilirubin, nitrite, ketones, protein, glucose, blood, urobilinogen and leukocyte esterase will be performed. If dipstick measurement results are positive (abnormal), microscopy would be assessed.

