8.4.2.5 Urinalysis

A clean-catch midstream urine sample will be obtained, in order to avoid contamination with epithelial cells and sediments, and allow proper assessments, as indicated in Table 8-1.

Parameters to be evaluated by urine dipstick test will include color, clarity, specific gravity, pH, glucose, protein, bilirubin, ketones, nitrite, leukocyte esterase, urobilinogen and blood. Standard microscopic evaluation of urinary sediments will be performed if the urine dipstick test shows abnormalities.

Microscopic Panel (Red Blood Cells, White Blood Cells, Casts, Crystals, Bacteria, Epithelial cells).

Urine for calculation of protein to creatinine ratio (PCR) or albumin to creatinine ratio (ACR) can be aliquoted from the clean-catch. (see Table 16-3).

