 - b. Whether the participant has resolution of NASH (absence of ballooning with no or minimal inflammation by histology) and no worsening of fibrosis at week 48 compared with baseline.
- 4. Summary measure: Odds ratio of participants achieving histological response at Week 48 for the following comparisons for each primary endpoint: combination vs. placebo, monotherapies vs. placebo, and combination vs. monotherapies.
- 5. Intercurrent events include
 - > Early discontinuation of study treatment before week 48 visit.
 - Non-histologic clinical event suggesting treatment failures (e.g bariatric surgery, liver transplant and death due to disease).
 - > Study treatment incompliance defined as relative dose intensity >1.25 or <0.75.
 - More than four weeks of cumulative exposure to any prohibited medications Section 6.2.2, alcohol usage more than what is permitted in the protocol, initiation of other T2DM or lipid lowering medication (e.g. GLP-1 modulator, statins), initiation of other treatment being evaluated or approved for NASH, or new concomitant interventions for weight control before the assessment for primary endpoint. The identification of relevant medications will be based on ATC3 and/or ATC5 codes, which will be included in analysis data set specifications. The list of concomitant interventions with significant effect for general weight loss will be determined based on blinded review of the study data.

For the intercurrent events related to the primary estimand, various strategies (such as treatment policy and composite variable) defined in ICH E9 (R1) will be utilized for the analyses. For instance, participants who discontinue the treatment after Week 24 will be asked to have their biopsies assessed at Week 48 regardless of the intercurrent event (treatment policy strategy), participants who discontinue the treatment before Week 24 will be considered as non-responders (composite variable strategy), and participants who have no biopsies extracted at Week 48 will be considered as non-responders (composite variable strategy).

Novartis	Confidential	Page 135 of 160
Amended Protocol Version 02 (Clean)		Protocol No. CLJN452D12201C

For non-intercurrent event missing data, certain multiple imputation methods will be applied to estimate the endpoints.

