12.4.3 Handling of remaining intercurrent events of primary estimand

Intercurrent events of primary estimand will be addressed with various strategies (given that these events occur before the histological assessments at Week 48):

- 1. Bariatric surgery: participants who have undergone bariatric surgeries during trial participation are considered as non-responders (composite variable strategy).
- 2. Use of alcohol above protocol permitted amount: the intercurrent events (overuse of alcohol) will be ignored for estimation (treatment policy strategy).
- 3. Addition or removal of any medication that may have a confounding effect on the endpoints: the treatment effect will be assessed with the intercurrent event ignored (treatment policy strategy). The treatment policy strategy may not be ideal if the confounding medications highly affect the endpoints. Consequently, a supplementary analysis will be conducted where the treatment effect is imputed as if the intercurrent event doesn't occur (hypothetical strategy)
- 4. Premature discontinuation of study treatment due to tolerability, efficacy, adherence, or adverse event: participants who discontinue the treatment after Week 24 will be asked to have their biopsies assessed at Week 48 regardless of the intercurrent event (treatment policy strategy), participants who discontinue the treatment before Week 24 will be considered as non-responders (composite variable strategy), and participants who have no biopsy extracted at Week 48 will be considered as non-responders (composite variable strategy).
- 5. Death, transplantation and other clinical outcomes: participants will be considered as non-responder (composite endpoint strategy).
- 6. Acute medical condition not related to the study treatment affecting the liver: participants will have their Week 48 biopsies assessed regardless of the intercurrent events (treatment policy strategy).
- 7. Acute medical condition related to the study treatment affecting the liver: participants are considered as non-responder (composite endpoint strategy).

Novartis	Confidential	Page 139 of 160
Amended Protocol Version 02 (Clean)		Protocol No. CLJN452D12201C

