16.1 Appendix 1: Clinically notable laboratory values and vital signs

The central laboratory will flag laboratory values falling outside of the normal ranges on the central laboratory reports. Investigators are responsible for reviewing these abnormal values for clinical significance, signing the laboratory reports to indicate their review, and reporting values considered clinically significant in the appropriate eCRF. Any clinically significant abnormal laboratory value should be evaluated and followed-up by the investigator until normal or a cause for the abnormality is determined.

SEE APPENDIX 16.2 FOR SPECIFIC LIVER EVENT AND LABORATORY TEST TRIGGER DEFINITIONS AND FOLLOW-UP REQUIREMENTS.

For ECGs, a notable QTc value is defined as a QTcF (Fridericia) interval of \geq 450 msec for males or \geq 460 msec for females, all such ECGs will be flagged by the Central CRO and require assessment for clinical relevance and continuance of the participant by the Investigator.

For vital signs, please see Table 16-1 for notable abnormalities.

Vital signs		Nota	Notable abnormalities		
	Absolute		Relative to baseline		
Pulse rate (beats/min)	> 130 < 40	> 120 and increase from baseline ≥ 15		
			≤ 50 and decrease from baseline ≥ 15		
Blood pressure (mmHg)	Systolic	> 200 < 75	\geq 180 and increase from baseline \geq 20		
			≤ 90 and decrease from baseline ≥ 20		
	Diastolic	> 115 < 40	≥ 105 and increase from baseline ≥ 15		
			≤ 50 and decrease from baseline ≥ 15		

Table 16-1 Vital signs

Note: these notable ranges should not be used as reference ranges to establish a clinical diagnosis

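### The visible protocol does not mask post-baseline urine glucose from sites and the trial team, although licogliflozin causes glucosuria

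*Protocol*

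**What the plan says.** **Measurement.** Section 8.4.2.5 lists the panel: "Parameters to be evaluated by urine dipstick test will include color, clarity, specific gravity, pH, glucose, protein, bilirubin, ketones". Table 8-1 footnote 10 repeats it with glucose included and no exception after baseline: "Dipstick measurements for color, clarity, specific gravity, pH, bilirubin, nitrite, ketones, protein, glucose, blood, urobilinogen and leukocyte esterase will be performed". The urinalysis row of Table 8-1 is labelled central. It is marked at both screening visits, Baseline, Weeks 2, 4, 8, 12, 16, 20, 24, 32, 40 and 48, and the Week 52 follow-up. Footnote 10 adds: "If dipstick measurement results are positive (abnormal), microscopy would be assessed".

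**Pharmacology.** Section 1.1.4 reports that "single and multiple doses of licogliflozin induced glucosuria in healthy volunteers", and the same sentence extends this to participants with T2DM. Table 6-3 prohibits other SGLT2 and SGLT1/2 inhibitors, which removes one alternative cause of a positive reading.

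**Reporting.** Section 16.1 states: "The central laboratory will flag laboratory values falling outside of the normal ranges on the central laboratory reports". Investigators must review those abnormal values and sign the reports. Section 8.4.2 leaves the details of result reporting to the central laboratory manual.

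**Blinding.** Section 6.4 requires participants, investigator staff, assessors and the sponsor's trial team to stay blinded. The methods visible there are confidentiality of the randomization data and matched placebo: "The identity of the treatments will be concealed by the use of placebo that are each identical in packaging". The public text of that list starts at item 2. No visible item concerns laboratory results.

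**SAP.** SAP Section 5.3.1 counts new dipstick glycosuria of 1+ or more as a nephrotoxicity criterion and attributes it to protocol renal monitoring. Protocol Table 16-3 has dipstick triggers for protein and blood, but none for glucose.

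**The concern.** A double-dummy design hides which tablet a participant takes. It does not hide a laboratory result that the drug itself changes. Each participant has pre-dose readings, so a turn from negative to positive at Week 2, repeated over 10 visits, is an easy cue. The more obvious symptom cue is weaker at this dose: in the NASH study summarised in Section 1.1.4, diarrhoea was reported by similar numbers on placebo and on 30 mg.

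What is at stake is not the histology score, which a central reader assigns (Section 8.3.2), but the steps around it that sites and participants control. Under Section 12.4.3, stopping treatment before Week 24 makes a participant a non-responder, and so does having no Week 48 biopsy after premature discontinuation. The same section says: "Acute medical condition related to the study treatment affecting the liver: participants are considered as non-responder". If the condition is judged unrelated, the biopsy is used. About 20% of Week 48 biopsies are expected to be missing (Section 12.8.1), so there is room for differential loss. Adverse-event causality and reporting, and diet and exercise counselling, are exposed too. The list of weight-loss interventions "will be determined based on blinded review of the study data"; that review is less blind if the trial team sees urine glucose.

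**Working it through.** The plan states no figure on this point, so there is none to reproduce. The check is a count, a sorting calculation and an illustration.

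**1. Exposure.** On-treatment visits with central urinalysis (Table 8-1): Weeks 2, 4, 8, 12, 16, 20, 24, 32, 40, 48 = 10 of 10.

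**2. The split.** Arm sizes (Section 3): A 140, B 80, C 80, D 80. Licogliflozin arms A + C = 140 + 80 = 220. Others B + D = 80 + 80 = 160. Total 380.

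**3. Comparisons affected.** Section 12.4.2 lists five comparisons per endpoint. The split separates the two arms in combination vs placebo, licogliflozin vs placebo and combination vs tropifexor. It does not in tropifexor vs placebo or combination vs licogliflozin. So 3 of 5 are affected, and over two endpoints 6 of 10. The six include both combination-versus-placebo tests, which decide study success.

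**4. How well a reading would sort participants.** The documents give no rate of positive dipsticks at 30 mg. Assume a positive reading in a share *s* of A + C (80% to 99%) and a share *f* of B + D (5% to 30%).

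Correctly sorted = [220*s* + 160(1 − *f*)] / 380

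- Worst case, *s* = 0.80, *f* = 0.30: (176 + 112)/380 = 75.8%
- Middle case, *s* = 0.90, *f* = 0.15: (198 + 136)/380 = 87.9%
- Best case, *s* = 0.99, *f* = 0.05: (217.8 + 152)/380 = 97.3%
- Always guessing A or C: 220/380 = 57.9%

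**5. Illustration of a route to the primary endpoint.** Assumptions: no true effect; combination 140 vs placebo 80; each endpoint tested at two-sided 2.5% (critical z = 2.241); 5 or 10 points more loss on placebo because of the cue; all of that loss scored as non-response.

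Placebo rate = p × (1 − extra loss). SE = √[p₁(1 − p₁)/140 + p₂(1 − p₂)/80]. Chance of a false win for the combination = 1 − Φ(2.241 − (p₁ − p₂)/SE). With no differential loss this is 1.25%.

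| Endpoint | Combination | Placebo | SE | False win |
|---|---|---|---|---|
| Fibrosis, 5 points | 20% | 19% | 0.0554 | 2.0% |
| Fibrosis, 10 points | 20% | 18% | 0.0547 | 3.0% |
| NASH resolution, 5 points | 10% | 9.5% | 0.0414 | 1.7% |
| NASH resolution, 10 points | 10% | 9% | 0.0408 | 2.3% |

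The base rates of 20% and 10% are the placebo assumptions in Table 12-3. The extra loss has no source in the documents.

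**6. Use of the reading.** Table 16-3 has no glucose trigger. The hypoglycaemia section (10.2.3.5) works from symptoms and measured glucose levels, and the ketoacidosis section (10.2.3.7) from symptoms, ketones, electrolytes and anion gap. None names urine glucose. The visible uses are reflex microscopy (Section 8.4.2.5, footnote 10) and the SAP criterion.

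**The case against.** The strongest reply is that the protocol never says urine glucose is released. Reporting rules sit in a laboratory manual that is not public, and item 1 of the blinding list is not visible. A reader might infer that results go to sites unmasked; the documents support only the weaker statement that nothing visible withholds them. That stands. Pointing the other way, the SAP ties dipstick glycosuria to renal monitoring, which suggests the field was meant to be seen.

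A reader might also infer that the double blind cannot hold. That is too strong. The cue gives two groups, not four arms. Of the 160 participants outside the licogliflozin arms, 80 take tropifexor, so a negative reading does not identify placebo. Participants with type 2 diabetes and HbA1c below 9.0% are eligible, so some glucosuria in Arms B and D is plausible. Nothing suggests that the central reader sees urinalysis.

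Two further routes should not be claimed. Added or removed confounding medication is ignored in the primary analysis (treatment policy, Section 12.4.3 item 3), so it does not by itself set response status. The no-biopsy rule sits under premature discontinuation, while missing values unrelated to intercurrent events are multiply imputed (Section 12.4.4). Automatic non-response for a treatment completer who declines biopsy is therefore not established.

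Finally, other cues remain: weight, genital infection, and self-monitored glucose in diabetic participants. Masking one field reduces the cue but does not remove every one.

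**Conclusion.** The point holds as a cheap improvement. The visible plan measures a direct pharmacological marker of licogliflozin at every on-treatment visit, has investigators sign central laboratory reports, and states no exception for that marker. Run as written, it would let sites and the trial team sort 220 participants from 160 with good but imperfect accuracy: 76% to 97% under the assumed ranges. The split bears on 6 of 10 primary comparisons.

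The size of any resulting bias is unknown. The false-win figures of about 2% to 3% (1.7% to 3.0% across the two endpoints), against a nominal 1.25%, show only what an assumed 5 to 10 point differential loss would do. They fix the direction, score all extra loss as non-response, and are not a forecast for this trial. The conclusion also assumes that neither the laboratory manual nor the non-visible blinding text already masks the result.

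**What to change.** In Sections 6.4 and 8.4.2.5 and Table 8-1 footnote 10, state that post-baseline urine glucose is withheld from reports to sites and to the blinded trial team until database lock, and is available to the independent analysts who serve the DMC. If the laboratory manual or other blinding text already does this, one sentence in Section 6.4 confirming it closes the point.

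Leave the other dipstick fields visible. Arrange laboratory reporting so that microscopy prompted by glucose alone does not reveal the masked result, without changing any clinical safety trigger. Reconcile the dipstick-glycosuria criterion in SAP Section 5.3.1 with protocol Table 16-3, since the criterion would mainly pick up an expected drug effect, and run any analysis of it after lock.

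The cost is a central-laboratory report setting, a data-transfer specification and short edits to the protocol, laboratory manual and SAP. The downside is that sites lose a reading that no visible site-action rule uses, and the other cues named above remain.

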8.4.2.6 Hepatitis markers

At screening, the presence of hepatitis C virus (HCV) will be by detection of HCV antibody (Ab). If HCV antibody (Ab) is not detected, participant can continue through the screening process. If HCV antibody (Ab) is detected, reflex test to the polymerase chain reaction (PCR) test for hepatitis C virus RNA will be performed. If HCV RNA is not detected in PCR, participant can continue through the screening process. Presence of HCV RNA is exclusionary.

At Screening, assay for presence of Immunoglobulin M (IgM) Hepatitis A antibodies (IgM anti-HAV) will be performed. Presence of IgM anti-HAV is exclusionary. No further testing is needed.

At Screening, assay for presence of hepatitis B surface antigen (HBsAg) will be performed. Presence of HBsAg is exclusionary. No further testing is needed.

Novartis	Confidential	Page 111 of 160
Amended Protocol Version 02 (Clean)		Protocol No. CLJN452D12201C

Hepatitis A, B or C serology will be assessed as indicated in Table 8-1 and if deemed appropriate, hepatitis serology will be assessed for liver safety monitoring as indicated in Section 10.2.1.

